9.1 Specification of Safety Parameters

9.1.1 Unanticipated Problems

Participation in this study meets minimal risk criteria consistent with 45 CFR 46. Thus, safety monitoring for this study will focus on unanticipated problems involving risks to subjects, including unanticipated problems that meet the definition of a serious adverse event.

The Office for Human Research Protections (OHRP) considers unanticipated problems involving risks to subjects or others to include, in general, any incident, experience, or outcome that meets **all** of the following criteria:

- unexpected in terms of nature, severity, or frequency given (a) the research procedures that are described in the protocol-related documents, such as the IRB-approved research protocol and informed consent document; and (b) the characteristics of the subject population being studied;
- related or possibly related to participation in the research ("possibly related" means there is a reasonable possibility that the incident, experience, or outcome may have been caused by the procedures involved in the research); and
- suggests that the research places subjects or others at a greater risk of harm (including physical, psychological, economic, or social harm) than was previously known or recognized.

Incidents or events that meet the OHRP criteria for unanticipated problems require the creation and completion of an unanticipated problem report form. Pls will complete the

following information when reporting an adverse event, or any other incident, experience, or outcome as an unanticipated problem to the IRB:

- appropriate identifying information for the research protocol, including the title, investigators' names, and the IRB project number;
- a detailed description of the adverse event, incident, experience, or outcome;
- an explanation of the basis for determining that the adverse event, incident, experience, or outcome represents an unanticipated problem;
- a description of any changes to the protocol or other corrective actions that have been taken or are proposed in response to the unanticipated problem.

To satisfy the requirement for prompt reporting, unanticipated problems will be reported using the following timeline:

- Unanticipated problems that are serious adverse events will be reported to the IRB and to NIDCR within 1 week of the investigator becoming aware of the event.
- Any other unanticipated problem will be reported to the IRB and to NIDCRwithin 2 weeks of the investigator becoming aware of the problem.
- All unanticipated problems should be reported to appropriate institutional officials
 (as required by an institution's written reporting procedures), the supporting
 agency head (or designee), and OHRP within one month of the IRB's receipt of
 the report of the problem from the investigator.

All unanticipated problems will be reported to NIDCR's centralized reporting system via Rho Product Safety:

• Product Safety Fax Line (US): [name]

Product Safety [contact]

Product Safety Email: rho [contact]

General questions about SAE reporting can be directed to the Rho Product Safety Help Line (available 8:00AM – 5:00PM Eastern Time):

9.1.2 Adverse Events

An adverse event is any untoward or unfavorable medical occurrence in a human subject, including any abnormal sign (for example, abnormal physical exam or laboratory finding), symptom, or disease, temporally associated with the subject's

participation in the research, whether or not considered related to the subject's participation in the research.

9.1.3 Serious Adverse Events

A serious adverse event (SAE) is one that meets one or more of the following criteria:

- Results in death
- Is life-threatening (places the subject at immediate risk of death from the event as it occurred)
- Results in inpatient hospitalization or prolongation of existing hospitalization
- Results in a persistent or significant disability or incapacity
- Results in a congenital anomaly or birth defect
- An important medical event that may not result in death, be life threatening, or require hospitalization may be considered an SAE when, based upon appropriate medical judgment, the event may jeopardize the subject and may require medical or surgical intervention to prevent one of the outcomes listed in this definition.

9.2 Time Period and Frequency for Event Assessment and Follow-Up

Unanticipated problems will be recorded in the data collection system throughout the study.

The PI will record all reportable events with start dates occurring any time after informed consent is obtained until 7 (for non-serious AEs) or 30 days (for SAEs) after the last day of study participation. At each study visit, the investigator will inquire about the occurrence of AE/SAEs since the last visit.

Any AE meeting the specified Serious Adverse Event criteria will be submitted on an SAE form to NIDCR's centralized safety system via Rho Product Safety. This report may be sent by fax or email. Once submitted, Rho Product Safety will send a confirmation email to the investigator within 1 business day. The investigator should contact Rho Product Safety if this confirmation is not received. This process applies to both initial and follow-up SAE reports.

SAE Reporting Contact Information:

Product Safety Fax Line (US): [name]

Product Safety [contact]

Product Safety Email: [contact]

......

General questions about SAE reporting can be directed to the Rho Product Safety Help Line (available 8:00AM – 5:00PM Eastern Time):

The study clinician will complete a Serious Adverse Event Form and submit via fax or email within the following timelines:

- All deaths and immediately life-threatening events, whether related or unrelated, will be recorded on the Serious Adverse Event Form and submitted to Product Safety within 24 hours of site awareness.
- Serious adverse events other than death and immediately life-threatening events, regardless of relationship, will be reported by fax within 72 hours of site awareness.

All SAEs will be followed until resolution or stabilization.

9.3 Characteristics of an Adverse Event

9.3.1 Relationship to Study Intervention

To assess relationship of an event to study intervention, the following guidelines are used:

- 1. Related (Possible, Probable, Definite)
 - a. The event is known to occur with the study intervention.
 - b. There is a temporal relationship between the intervention and event onset.
 - c. The event abates when the intervention is discontinued.
 - d. The event reappears upon a re-challenge with the intervention.
- 2. Not Related (Unlikely, Not Related)
 - a. There is no temporal relationship between the intervention and event onset.
 - b. An alternate etiology has been established.

9.3.2 Expectedness of SAEs

The NIDCR Medical Monitor and the Study PIs will be responsible for determining whether an SAE is expected or unexpected. An adverse event will be considered unexpected if the nature, severity, or frequency of the event is not consistent with the risk information previously described for the intervention.

9.3.3 Severity of Event

The following scale will be used to grade adverse events:

- 1. Mild: no intervention required; no impact on activities of daily living (ADL)
- Moderate: minimal, local, or non-invasive intervention indicated; moderate impact on ADL
- 3. Severe: significant symptoms requiring invasive intervention; subject seeks medical attention, needs major assistance with ADL

9.4 Reporting Procedures

The UCHC IRB requires reporting of unexpected adverse events that may represent an unanticipated problem involving risks to subjects or others (UPIRSO). Such events are to be reported using the *Problem Report Form* available on the UCHC website. Upon review the Institutional Review Board (IRB) may require changes to informed consent forms and/or protocols or other actions such as increased monitoring. The IRB makes the final determination as to whether an internal adverse event constitutes an unanticipated problem and whether changes to the consent and/or protocol are required. For external events, the sponsor should indicate if they have deemed the event to be a UPIRSO, and if so the IRB is to be informed.

All investigators and study personnel must be familiar with the policy for reporting unanticipated problems, inclusive of unexpected adverse events that may be unanticipated problems, to the IRB. All policies are available on the UCHC website. Such events must be reported using the Problem Report Form within 5 working days (7 calendar days) of becoming aware of the event. See Section 9.3.

9.4.1 Unanticipated Problem Reporting to IRB and NIDCR

Reporting unanticipated problems to the IRB is discussed in Sections 9.1.1 and Section 4. As with reporting requirements for the IRB, the PI will record all reportable events with start dates occurring any time after informed consent is obtained until 7 (for non-serious AEs) or 30 days (for SAEs) after the last day of study participation. At each study visit, the investigator will inquire about the occurrence of AE/SAEs since the last visit. Events will be followed for outcome information until resolution or stabilization. These events will be reported in writing to NIDCR within 5 working days for serious adverse events and within one month for non-serious adverse events.

9.4.2 Serious Adverse Event Reporting to NIDCR

Any AE meeting the specified Serious Adverse Event criteria will be submitted on an SAE form to NIDCR's centralized safety reporting system via [contact]. See section 9 of the MOP for SAE reporting requirements.

9.5 Halting Rules

Study halting may occur as required by the IRB or NIDCR. The study PIs may temporarily suspend enrollment pending review by these authorities if warranted based on the presence, type, or frequency of SAEs or other changes in the study protocol which may place participants in greater than anticipated risk.

10 STUDY OVERSIGHT

The Principal Investigators, [name], Pls on the prior NIDCR funded studies, will be responsible for study oversight, including monitoring safety, ensuring that the study is conducted according to the protocol and ensuring data integrity. The Pls will review the data for safety concerns and data trends at regular intervals, and will promptly report to the IRB and NIDCR any Unanticipated Problem (UP), protocol deviation, or any other significant event that arises during the conduct of the study.

In addition to the PIs responsibility for oversight, study oversight will be under the direction of the NIDCR Medical Monitor. The PIs will submit a report every 6 months to the NIDCR Medical Monitor for review. This report will include data regarding enrollment and retention, unanticipated problems and protocol deviations, outcome measures, quality management findings and other relevant parameters. If necessary, additional steps may be taken to ensure data integrity and protocol compliance.

The field team will be directed by the intervention coordinator and the survey coordinator. Both will work closely with the data analyst who will be responsible for tracking field progress and reporting to the study team. The PIs will remain in close contact with the field administrative team.

It is our practice for the research team to meet weekly and this group functions as a steering committee. We discuss and monitor: the general design and conduct of the study: preparation of the essential study documents, including the protocol, protocol amendments, MOP and data collection forms; review of data collection practices and procedures; changes in study procedures as appropriate; allocation of resources based on priorities of competing study demands; review of study progress and implementation of necessary steps to ensure the achievement of study goals; review and implementation of recommendations from those responsible for safety monitoring. We submit a monthly report electronically to the NIDCR program officers to keep them advised of our progress.

11 CLINICAL SITE MONITORING

Clinical site monitoring will not be done for this study; however, the NIDCR reserves the

right to conduct independent audits or clinical monitoring as necessary.

12 STATISTICAL CONSIDERATIONS

12.1 Study Hypotheses

- 1. The AMI-PM will produce better short term (T1) clinical outcomes than the Campaign (CA+PM) (AIM 1).
- 2. The CA+PM+AMI-PM will produce better mid-term (T2) and long-term (T3) clinical outcomes than the AMI-PM+CA+PM (AIM 2).
- 3. The AMI-PM will produce more change in mediating cognitive domains than the CA+PM.
- 4. Both AMI-PM+CA+PM and CA+PM+AMI-PM will result in no differences in change in mediating cognitive domains from T0 to T2.
- The greater the dosage (proportion of total talking points recorded for all domains in a tailored AMI; and exposure to campaign activities and messages), the better the outcomes.
- 6. We will investigate an exploratory hypothesis examining the effects of the intervention and sequence on oral health quality of life (a secondary outcome), as well as on clinical outcomes.

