4 STUDY DESIGN

Overall Design: The study utilizes a modified fractional factorial design (MFFD) which compares the short term outcomes of the two intervention components: the tailored individual level brief intervention (AMI-PM) and the group level Campaign including embedded oral health skills development through practice-to-mastery (CA+PM). It also evaluates the effects of differential sequencing of these modes of delivery components in relation to short and longer term outcomes. Finally, it evaluates intervention mechanisms through mediational modeling of the cognitive and the behavioral components over time. The two intervention components are the individualized AMI-PM (Component A), and the group CA+PM (Component B). To evaluate sequencing we will randomize pairs of senior residences into two conditions: Condition 1 and Condition 2. Buildings in Condition 1 will initiate with Component A, followed by Component B. Buildings in Condition 2 will initiate with Component B, followed by Component A. This study design will allow us to compare the AMI-PM outcomes to CA+PM short term outcomes, and to determine which condition sequence (A+B or B+A) will produce the best clinical outcomes. Each of 3 cycles of Condition 1 (A+B) compared to Condition 2 (B+A) will take place over a 16-18 month period each in two matched buildings with an N of 60 per building (N per cycle of 120; total N for all three cycles approximately 360). We anticipate an attrition rate of approximately 25% and a final N of approximately 270 by the T3 measure, 135 in Condition 1 and 135 in Condition 2. Primary outcomes are improvements in gingival health and decreases in plaque scores.

A description of the study population: Participants will be recruited from low income senior housing in Central Connecticut. The population consists of independent living older adults many of whom have chronic health conditions. Residents also include adults less than 62 years of age residing in these buildings who are disabled. Residents must meet income guidelines and be over the age of 62 or be disabled children and adults between the ages of 18 and 61.

Methods for collecting data for assessment of study objectives: Data collection will consist of clinical assessment, and surveys evaluating changes in cognitive domains (See Section 16).

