Intervention variables: As all subjects are exposed to the same interventions, it is of interest to unpack the intervention into 1) dosage (percent of talking points covered for all focal points (domains) addressed in the intervention, and 2) exposure to focal point messages during campaigns. Study Hypothesis #5, regarding dosage of interventions, will be assessed by creating an ordinal scale that measures an individual's exposure to talking points through participation in the AMI and exposure to messages via campaigns, thus creating a measure of dosage. We will then assess if dosage predicts better outcomes. This can be done directly (e.g., compare mean gingival scores across dosage levels with ANOVA) or dosage can be used as a predictor variable in the statistical models and causal pathway analyses. Oral health skills/Practice-to-Mastery (a 4 point Likert scale) and focal points (count variable) can be analyzed using similar techniques and approaches.

MFFD layout: N at the beginning of study			
	Sequence	N	
Building 1	A:B	60	
Building 2	B:A	60	
Building 3	A:B	60	
Building 4	B:A	60	
Building 5	A:B	60	
Building 6	B:A	60	

Secondary Outcome of General Oral Health Assessment Inventory (GOHAI): We will conduct a set of secondary analyses with GOHAI as a continuous outcome. It will also be incorporated into our statistical/mediator models as predictor to see if it acts as an effect modifier.

Cognitive Mediators: The following variables will be incorporated into the causal pathway analysis to address example hypotheses #3 and #4: knowledge, oral health beliefs/norms, social support, oral hygiene behaviors, fears/worries, practice to mastery, and behavioral intentions. We will use longitudinal mediation to compared the efficacy of AMI-PM+CA+PM to CA+PM+AMI-PM in terms of whether they differ significantly in the amount of change that they engender in the gingival index and plaque score, indirectly through the mediators measured in our model.

outcomes.

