The classical Barron & Kenny (1986) mediation approach to longitudinal mediation would examine whether the intervention impacts the levels of our mediators, such as beliefs, at T1 (for example), which in turn affect clinical outcome measures resulting from participant behaviors as measured by the Gingival index and Plaque Scores at T2. Or, simply put, whether levels of self-efficacy at T1 are associated with the levels of gingival index scores at T2 indirectly through self-efficacy at T1 (and other mediators previously referenced). But, we are interested in examining whether there is a change in our mediators over time, and if so, whether this change significantly leads to a change in behaviors, as assessed by the Gingival Index and Plaque Scores. Recent methodological studies actually show that the analysis of change is more appropriately captured by specifying change (differences) in self-efficacy and our other mediators and behavioral outcomes between adjacent time points (i.e. T1-T0, and T2-T1) as latent difference scores, and explicitly modeling these change scores to represent dynamic change, i.e., the impact of change in the mediators on change in the behavioral

Hypothesis #3 will be tested using latent change score analysis specifying AMI and Campaign as predictors of change in behavioral beliefs(ΔBB), OH social support (ΔSS), locus of control beliefs(ΔCB), self-efficacy(ΔSE), fears/worries ($\Delta F/W$), social norms (ΔSN), and behavioral intentions (ΔSI) from baseline to first and second follow-up.

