To test hypothesis #4, we will conduct dynamic mediation using latent change (difference) score (LCS) mediation analysis. The analyses will be conducted in Mplus 7 where change (difference) scores representing differences in each mediator and outcome variable from baseline to final follow up (i.e. T1-T0 (ΔT_{10}), and T2-T1(ΔT_{21}) will be generated. It is the difference scores of the mediators and outcome variables that are modeled. Generally speaking, causal paths specifying latent (true) change, represented by change in knowledge, oral health beliefs/norms, OH social support, oral hygiene behaviors, fears/worries, oral health practice to mastery skills, and behavioral intentions in going from T0 to T1, and T1 to T2 will be specified, to predict change in Gingival Index and Plaque Scores at T2 (i.e., ΔGingival Index₂₁, ΔPlaque score₂₁). For example, we will test whether change in fears/worries from T0 to T1 significantly predicts changes in Gingival Index and Plague Scores at final follow-up, T2 (ΔGingival Index₂₁, Δ Plague scores₂₁). To assess the impact of the change in self-efficacy (Δ SE). on changes in Gingival Index scores (ΔGingival Index), direct and indirect paths from change in self-efficacy from baseline to first follow up (ΔSE₁₀) that predict the change in Gingival Index at the final follow-up (ΔGingival Index₃₀) will be specified and tested. Select direct and indirect paths from change scores of the other mediator variables to change scores of behavioral outcomes will also be specified in a similar fashion, and all these relationships will be tested simultaneously.

Summary: Using a conservative set of assumptions and based on our own pilot data, we have demonstrated, using our pilot data estimates, that we will have sufficient power to detect significant changes, using a two-group t-test which makes minimal

IRB Review
IRB NUMBER: 14-188-6
IRB APPROVAL DATE: 01/03/2019
12/14/2018

Good Oral Health: A Bi-level Intervention to Improve Older Adult Oral Health Protocol #14-046-E

assumptions about the data. It is worth noting that the proposed statistical models have greater power characteristics than the t-tests used to calculate power.

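### Hypothesis 4 compares the two sequences on T0–T2 mediator change, but its assigned model writes only mediator-to-outcome paths, and the closest contrast is labelled Hypothesis 3

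*Combined protocol and SAP*

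**What the plan says.** **The hypothesis.** Section 12.1, item 4: "Both AMI-PM+CA+PM and CA+PM+AMI-PM will result in no differences in change in mediating cognitive domains from T0 to T2". The quantity is a difference between the two sequences in mediator change, and the horizon is T0 to T2.

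**The analysis assigned to it.** Section 12.4: "To test hypothesis #4, we will conduct dynamic mediation using latent change (difference) score (LCS) mediation analysis". The general description has change in the mediators from T0 to T1 and T1 to T2 used "to predict change in Gingival Index and Plaque Scores at T2". The fears/worries example, the self-efficacy example and the closing sentence on the remaining mediators run in the same direction.

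**The analysis assigned to Hypothesis 3.** Section 12.4: "Hypothesis #3 will be tested using latent change score analysis specifying AMI and Campaign as predictors of change" in a list of mediators, "from baseline to first and second follow-up". In Section 12.1, Hypothesis 3 is directional (AMI-PM produces more mediator change than CA+PM) and gives no time point.

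**The overview.** The Cognitive Mediators paragraph of Section 12.4 brings variables into the causal pathway analysis "to address example hypotheses #3 and #4". It then compares the two sequences "in terms of whether they differ significantly in the amount of change that they engender in the gingival index and plaque score", acting indirectly through the mediators.

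**The design.** Section 4: "Buildings in Condition 2 will initiate with Component B, followed by Component A"; Condition 1 has the reverse order. Appendix A schedules the survey at T0, T1 and T2 in both conditions, with both components offered before T2.

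**Practice to mastery.** Section 12.4 lists it among the cognitive mediators, mentions it again under Intervention variables, and includes T0–T1 and T1–T2 change in these skills in the Hypothesis 4 model. Footnote 1 in Section 6 records an approved request to remove the skills assessment as a mediating measure. Footnote 2 in Section 8.1, Section 13 and Section 16.3 say that the skills data will not be used to measure change, for evaluation, or for outcome analysis.

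**The concern.** A hypothesis about how sequence affects mediators needs an estimate of the sequence effect on mediators. The model named for Hypothesis 4 is written as a set of effects of mediators on outcomes, which is a different quantity. A team following the text would finish the Hypothesis 4 analysis without a stated result for Hypothesis 4. The result nearest to it would appear under Hypothesis 3, which makes a different and directional claim.

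Two things follow. First, the hypothesis predicts no difference, and the plan does not say how such a result will be reported. With six buildings in three pairs, a non-significant contrast carries little information. Second, the model as written includes a variable that the protocol has withdrawn as a mediator, so the mediator set is not settled.

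**Working it through.** **1. Hypothesis against model.**

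| Text in Sections 12.1 and 12.4 | Predictor | Response | Horizon |
|---|---|---|---|
| Hypothesis 4 | sequence | mediator change | T0–T2 |
| Model assigned to Hypothesis 4 | mediator change | clinical or behavioral outcome change | mainly T0–T1 mediator change to later outcome change |
| Model assigned to Hypothesis 3 | AMI / Campaign | mediator change | T0 to first and second follow-up |
| Overview for Hypotheses 3 and 4 | sequence, via mediators | clinical change | not stated |

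Only the third row has mediator change as the response. By T2 both conditions have been offered both components, so at second follow-up an AMI/Campaign arm contrast amounts to a sequence contrast. That is what Hypothesis 4 needs.

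**2. Can the written paths, or an indirect effect, stand in for it?** A simulation with assumed standardised paths (270 participants, 135 per sequence, 2,000 runs, clustering ignored) set *a* = sequence effect on mediator change and *b* = mediator effect on clinical change.

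- *b* = 0.4, *a* = 0 or 0.5: the mediator-to-clinical path is estimated at 0.40 and rejected in 100% of runs in both cases. It carries no information on *a*.
- *a* = 0.5, *b* = 0: the indirect effect is significant in 4.5% of runs; the direct sequence-to-mediator contrast is significant in 98.6%.
- *a* = 0.5, *b* = 0.4: the indirect effect is significant in 98.3% of runs. It follows the sequence effect only when the mediator also moves the outcome.

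**3. Mediator lists.** Section 3.2.3 includes perceived risks; the Section 6 framework and Section 12.4 do not. Knowledge and oral hygiene behaviors are in Sections 3.2.3 and 6 and in the Hypothesis 4 model, but not in the Hypothesis 3 list. Practice to mastery is in the Cognitive Mediators list and the Hypothesis 4 model, but not in Section 3.2.3, the Section 6 framework or the Hypothesis 3 list.

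**4. How informative would the right contrast be?** The plan gives no figure to reproduce for Hypothesis 4. Section 12.2 powers clinical outcomes in the first period only; that table does reproduce at 123 per group (0.20/0.47 gives 91.4% by t-test; stated 91). The following is illustration only.

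Inputs: 45 per building and 135 per arm (Section 12.2; Section 4 gives 135 as the T3 projection); ICC 0.01 and 0.02 (Section 12.2, borrowed from the clinical-outcome calculation). The documents give no mediator SD or effect, so the difference is assumed to be 0.5 SD of change.

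- Design effect = 1 + (45 − 1) × ICC = 1.44; 1.88
- Effective N per arm = 135 / design effect = 93.75; 71.81
- SE = √(2 / effective N) = 0.146; 0.167 SD
- Noncentrality = 0.5 / SE = 3.42; 3.00
- df = 2 × effective N − 2, or 6 buildings − 2 = 4, or 3 pairs − 1 = 2
- Non-significance from the noncentral t, two-sided α = 0.05
- Median 95% CI half-width = t × SE × √(median χ² / df); the last factor is 0.916 at 4 df and 0.833 at 2 df. Example at ICC 0.01, 2 df: 4.303 × 0.146 × 0.833 = 0.52

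| Test | True 0.5 SD difference non-significant (ICC 0.01 / 0.02) | Median 95% CI half-width, SD |
|---|---|---|
| Effective-N t-test | 7.4% / 15.5% | 0.29 / 0.33 |
| Buildings, 4 df | 27.3% / 38.2% | 0.37 / 0.42 |
| Three pairs, 2 df, no precision gain from matching | 53.7% / 61.3% | 0.52 / 0.60 |

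At the plan's own effective N of 123 per arm, the three percentages are 2.6%, 17.0% and 44.9%.

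**The case against.** The best defence is that the Hypothesis 4 paragraph should not be read alone. The overview introduces one pathway analysis for Hypotheses 3 and 4 and compares the sequences through the mediators. An indirect sequence effect cannot be estimated without a sequence-to-mediator path. The Hypothesis 4 paragraph also builds T0–T1 and T1–T2 change for each mediator, which sum to T0–T2 change, and it presents several of its paths as examples.

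This stands in part. A reader might infer that sequence will be left out of the fitted model; the documents do not support that, because the overview implies the path. What remains is that the contrast is not stated and that the comparison which is stated ends in clinical change. Step 2 shows that such an indirect effect can be null while the sequences differ on the mediator.

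A reader might also infer that the investigators will take a non-significant result as proof of no difference. No section says so. The gap is that no reporting rule is given.

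Finally, the figures in step 4 do not measure the mapping fault and would not change if it were corrected. That is right. They bear only on how a prediction of no difference should be reported, and the 2-df row assumes a pair-level analysis that the plan does not state.

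**Conclusion.** The point holds as a fault of assignment and specification. The written test for Hypothesis 4 targets mediator-to-outcome paths, the closest contrast is filed under Hypothesis 3, and the assigned model includes a variable withdrawn as a mediator. This rests on the text and needs no assumption; the practice-to-mastery conflict is a separate clean-up item and adds no weight to the mapping point.

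If the right contrast is run, an observed lack of difference will probably not support a claim of no difference. Under the stated assumptions, the median 95% interval extends about 0.3 to 0.6 SD either side of the estimate, depending on how building is handled.

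Hypotheses 1 and 2 and the primary outcomes are unaffected, and the T0 and T2 surveys needed are already scheduled. Confidence is moderate to high. The change should be made, but it is at the low end of that category.

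**What to change.** 1. Under Hypothesis 4, state the between-sequence contrast of T0–T2 change in each mediating domain, accounting for building. If the matched pairs are modelled, use the correspondingly few degrees of freedom (2 with three pairs). List the domains explicitly and do not borrow the Hypothesis 3 list; say whether knowledge, oral hygiene behaviors and perceived risks are included.
2. Report each domain's estimate with its 95% confidence interval, and state that no difference will not be concluded from non-significance. A pre-set equivalence margin is optional.
3. Keep the mediator-to-outcome paths under Objective 3, and keep the T0–T1 contrast under Hypothesis 3.
4. Remove practice-to-mastery change from the latent change score model. Reconcile its two other mentions in Section 12.4 (Cognitive Mediators and Intervention variables) with the Section 6 and 8.1 footnotes and Sections 13 and 16.3, and say whether any retained mention means only the in-session score that Section 16.3 keeps as process data.

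The cost is analysis-plan wording and one simple model per domain, with no new data. The downside is that the prediction of no difference will probably have to be reported as an estimate with its uncertainty. Even with a margin of ±0.5 SD and a true difference of zero, a simulated 90% interval falls inside the margin in 82–92% (effective-N), 61–76% (4 df) or 44–55% (2 df) of trials per domain under the same assumptions, and less often if every domain must pass.
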